5.1 Eligibility criteria

5.1.1 Inclusion criteria

- 5.1.1.1 Subjects who are willing and able to give informed consent for participation in the study.
- 5.1.1.2 Male and female subjects aged 18 years or above.
- 5.1.1.3 Diagnosed by the gastroenterology team with Crohn's disease (CD).
- 5.1.1.4 MRE imaging since 2015 for their CD.

5.1.2 Exclusion criteria

- 5.1.2.1 Subjects unwilling or unable to give informed consent.

5.2 Recruitment, consent and randomisation processes

5.2.1 Recruitment

5.2.1.1 Recruitment for the ProSpA-CD-Screen phase:

The gastroenterology team will write to patients with CD who have had MRE imaging since 2015 (estimated to be approximately 1100 patients) to ask them for consent to review their MRE imaging for evidence of axSpA. CD subjects with a known diagnosis of SpA will be eligible and invited to enter the study. Subjects who consent to this will then have their MRE imaging reviewed by a musculoskeletal radiology specialist registrar ([name]) and a rheumatology specialist registrar ([name]).

5.2.1.2 Recruitment for the ProSpA-CD-Assess phase:

Patients with lesions consistent with axSpA on the MRE (and no known diagnosis of SpA) will be informed by telephone and letter by the gastroenterology team and then be referred to [name] NHS SpA clinic *as per* standard of care. They will also be invited to enter the ProSpA-CD-Assess phase of the study at that time and consent will be taken during the clinic encounter.

CD subjects with a known diagnosis of SpA who are already under the care of a rheumatology team and have lesions on MRE consistent with axSpA will also be contacted by telephone and letter by the gastroenterology team. However, since they are already receiving standard NHS care for their SpA, they will be sent a separate invitation letter, PIS and reply slip (study interest form) by the gastroenterology team to attend the rheumatology SpA research clinic for assessment of axSpA by [name] outside of their routine NHS care. Informed consent for study participation will be performed at the start of the consultation.

Subjects (including those with a known diagnosis of SpA) who have consented to having their MRE scans reviewed, but who do not have lesions consistent with axSpA on MRE, will be informed in writing of this by the gastroenterology team. They will also be advised that they may be invited to enter this part of the study as a control subject if they are randomly selected through matching (age and sex) to the enrolled 'MRE+ cases' (1:1 ratio). Matched potential control subjects will then be sent an invitation letter, PIS and reply slip (study interest form) by the gastroenterology team to attend the rheumatology SpA research clinic to be assessed by [name] for clinical evidence of axSpA. Any CD subjects with a history of SpA who have been selected as a potential control subject will be sent a separate invitation letter, PIS and reply slip (study interest form) by the gastroenterology team. Informed consent for study participation will be performed at the start of the consultation in the SpA research clinic.

5.2.2 Consent

There will be two separate stages of informed consent.

5.2.2.1 Consent for retrospective review of the MRE scans (ProSpA-CD-Screen phase)

The gastroenterology team will write to all patients with CD and MRE scans since 2015 to ask for consent to review the images for evidence of axSpA. This correspondence will include a PIS and consent form with a stamped-addressed envelope for returns. The pack will also contain a BASDAI questionnaire with six simple questions relating to symptoms of axial inflammatory pain. These six questions, answered on a 1-10 VAS will pose low burden on the subject and be optional to complete, but will markedly help the research team gauge the impact of selection bias on the study given that there may be a preponderance of patients with axial pain willing to participate in the study.

5.2.2.2 Consent to enter the study as a case or control subject (ProSpA-CD-Assess phase)

Patients with lesions on MRE consistent with axSpA (and no known diagnosis of SpA) will be informed of this by the gastroenterology team (by telephone and letter) and be referred to [name] NHS SpA clinic for further clinical assessment. Once informed, they will also be invited by post to enter the research element of the study, with an invitation letter, accompanying PIS and reply slip (study interest form) with a stamped-addressed envelope to permit the patient to express if they do or do not wish to participate in the study.

CD subjects with a known diagnosis of SpA who are already under the care of a rheumatology team and have lesions on MRE consistent with axSpA will also be contacted by telephone and letter by the gastroenterology team. The subjects will then be sent a separate invitation letter, PIS and reply slip (study interest form) with a stamped-addressed envelope to permit the subject to express if they do or do not wish to participate further.

Subjects (including those with a known diagnosis of SpA) without evidence of axSpA on MRE will be contacted by the gastroenterology team (by letter) to inform them of the results and will also be advised that they may be invited to enter the study as a control subject. Once the cases have been identified and enrolled, control subjects will then be randomly selected (age and sex-matched in a case : control ratio of 1:1) to enter the research element of the study. The gastroenterology team will then write to these subjects to invite them to enter the study, accompanied by a PIS and a reply slip (study interest form) with a stamped-addressed envelope to permit the subject to express if they do or do not wish to participate further. Any CD subjects with a history of SpA who have been selected as a potential control subject will be sent a separate invitation letter, PIS and reply slip (study interest form) by the gastroenterology team.

During the clinic consultation for both cases and controls, the research study will be discussed further and the subject will be provided with the opportunity to ask any questions they may have regarding the study. If the subject subsequently agrees to take part in the study, then inclusion and exclusion criteria will be assessed and informed written consent will be taken.

6. Study schedule

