Subjects meeting the inclusion criteria and giving informed consent as per section 5.2.2 will then be recruited in to the ProSpA-CD-Assess phase of the study. Consented subjects will complete the following PROMs; BASDAI, BASFI, VASbp, ASDAS and HAQ-DI [37-40]. Each subject will be examined in the SpA clinic using the BASMI, 68 tender joint count, 66 swollen joint count, the SPARCC enthesitis index, and for skin or nail psoriasis. The following investigations will also be performed as per standard of care for the patients with axial skeleton abnormalities on their MRE (MRE+) and no known diagnosis of SpA, if clinically indicated and if not been performed in the preceding month; FBC, renal function, LFTs, CRP, ESR and faecal calprotectin. *HLA-B27* testing will also be requested if not previously performed. These investigations will also be performed for the control subjects and the group of CD subjects with a known diagnosis of SpA who are MRE+ (if not performed in the preceding month and if *HLA-B27* not previously performed) but will be funded by the research grant unless clinically indicated.

A dedicated axial MRI scan of the spine and sacroiliac joints will be performed in all case and control subjects if indicated by the clinical assessment. Subjects in whom a dedicated axial MRI scan is not clinically indicated, or those who have had one performed previously for a known diagnosis of SpA, will be consented to undertake the MRI scan for research purposes and the MRI scan will be funded by the research grant.

All subjects (cases and controls) will be asked to further consent to provide research samples, including whole blood and stool, for storage and future analysis (serum for biomarker analysis, plasma for proteomic analysis, DNA for genotyping, and stool for microbiome analysis). Collection of these samples will be funded by the existing research grant, and analysis will be funded by research grants that are currently being applied for.

The control group will receive no further follow up unless clinically indicated. CD subjects in this group with a known history of SpA will be followed up as planned by their primary rheumatology team.

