4.3 ProSpA-CD-Assess phase

4.3.1 Assessment of patients with lesions on MRE consistent with axSpA (cases)

Patients with lesions on MRE consistent with axSpA (and no known diagnosis of SpA) will be informed by telephone and letter by the gastroenterology team and referred to [name] NHS rheumatology SpA clinic. They will also be sent separately an invitation letter, participant information sheet (PIS) and reply slip (study interest form with a stamped-addressed envelope for returns) for the ProSpA-CD-Assess phase of the study by the gastroenterology team. CD subjects with a known diagnosis of SpA who are already under review by rheumatology and who have lesions on MRE consistent with axSpA will also be considered as cases and will be sent an invitation letter, PIS and study interest form. However, they will instead be invited to attend the rheumatology SpA research clinic to be assessed for axSpA (with the control group) as this will be considered to be outside of their routine NHS care.

In the NHS SpA clinic, the patients will be assessed by a single rheumatologist ([name], in a supernumerary capacity with salary funded by the research grant) for clinical evidence of axSpA *as per* standard of care using the 2009 ASAS criteria for axSpA, modified New York criteria for AS and CASPAR criteria for PsA (see Appendices 5, 6 & 7). The assessment will include a clinical history, examination (including BASMI, 68 tender joint count, 66 swollen joint count, the SPARCC enthesitis index and for skin or nail psoriasis), PROMs (BASDAI, BASFI, VASbp, ASDAS and HAQ-DI), blood samples (FBC, renal function, LFTs, CRP and ESR unless performed in the preceding month, and HLA-B27 unless previously performed) and stool samples (the monitoring of IBD luminal activity with faecal calprotectin is well established [41, 42]; stool samples will therefore also be collected to measure faecal calprotectin concentrations unless performed in the preceding month). During the consultation, the ProSpA-CD-Assess phase of the study will also be discussed further and patients will be provided with the opportunity to ask any questions they may have regarding the study. If they agree to participate in the study and meet the inclusion criteria, then written informed consent will be taken. The blood and stool tests will be performed as per standard of care if clinically indicated or for research and funded by the research grant if not clinically indicated.

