6.1 MRE Review

Subjects who consent for the ProSpA-CD-Screen phase of the study will have their MRE images reviewed for evidence of axSpA

Subjects who then consent for the ProSpA-CD-Assess phase of the study will immediately undergo the following assessments:

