6.7 Definition of the end of study

This will be the date of the last visit of the last participant

If a subject is unable to undertake these assessments immediately, a convenient future research clinic appointment will be made for them and associated travelling costs will be reimbursed.

This study schedule will pose low burden and inconvenience to the subject. Blood sampling will take place at the time of clinical measurements, and are of low total volume (40ml). The subjects will be asked to return to have the dedicated axial MRI scan and to minimise inconvenience, they will be encouraged to return their stool samples when they attend for the scan. Control subjects will be reimbursed for travel and parking costs, and the case subjects will also be reimbursed for any extra travel or parking costs incurred through participating in the study.

Clinical questionnaires are those that would be completed *as per* standard in usual clinical care (except for the control group). However, as we are asking questions in some of the PROMs about the subject's experience of illness, this may cause a degree of upset. Therefore to minimise distress, the clinician ([name]) will talk the subject through each questionnaire prior to completion at the initial clinic visit. In addition, our participation information sheets will stress that participation is voluntary and that the subject can withdraw from the study at any time without their care being affected. Our participation information sheets will also explain the processes taken to maintain anonymity and confidentiality.

The correspondence (invitation letters and PIS) for CD subjects with and without known SpA will have different content to reflect this and to reduce any potential concern or anxiety.

The MRI scan is a non-invasive procedure and the subjects will already have had the experience of having a MRI scan (MRE). However, some subjects may find it difficult to have the MRI scan if they suffer from claustrophobia. Therefore, the MRI scan procedure will be explained to the subject during the initial consultation and they will be provided with the opportunity to ask any questions. We will also emphasise that this is voluntary and that they have the right to decline this or any other part of the study.

7. Data collection, source data and confidentiality

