8.2 Statistical analysis

Statistical input has been sought from the University of Cambridge Statistics Clinic (PhD student [name] and his supervisor [name]) and will be supported by [name]. Inter- and intra-rater reliability testing will be performed for the MRE and axial MRI assessments using intra-class correlation coefficients (ICC). The proportion of CD cases with evidence of axSpA on MRE imaging who fulfil diagnostic criteria for axSpA will be expressed as a percentage. Further descriptive analyses will also be performed on study participants. Due to the possible preponderance of patients with axial pain willing to participate in the study and therefore selection bias, we will not be able to calculate the true prevalence of axSpA in CD patients.

As it is expected that the majority of data collected will be count data with an excess of zero-values, a zero-inflated Poisson (ZIP) regression model will be used to test for association between the presence of axSpA, MRE score, PROMs, clinical indices, site of CD and blood biomarkers. In addition, ZIP regression will be used to test for association between MRE scores and those of dedicated axial MRI scans. Zero-inflated binomial regression will be used as appropriate, where the mean approximates the variance. Two-tailed tests will be performed, and the alpha set at 0.05.

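### Section 8.2 should say which symptom scores are tested against MRE score, and use the BASDAI collected before each scan is read

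*Combined protocol and SAP*

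**What the plan says.** **The test.** Section 8.2 states that "a zero-inflated Poisson (ZIP) regression model will be used to test for association between the presence of axSpA, MRE score, PROMs, clinical indices", among other variables. It adds: "Two-tailed tests will be performed, and the alpha set at 0.05". It does not say at which time point the PROMs are taken.

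**The PROMs.** Section 4.1, describing subjects recruited to the Assess phase, says: "Consented subjects will complete the following PROMs; BASDAI, BASFI, VASbp, ASDAS and HAQ-DI". Section 6.1 places them after the MRE review: "Subjects who then consent for the ProSpA-CD-Assess phase of the study will immediately undergo the following assessments". Section 6.7 adds that the clinician "will talk the subject through each questionnaire prior to completion at the initial clinic visit".

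**What patients know by then.** Under section 4.3.1, MRE-positive patients without known SpA "will be informed by telephone and letter by the gastroenterology team" and are referred to the NHS SpA clinic. Sections 5.2.1.2 and 5.2.2.2 have MRE-positive patients with known SpA contacted by the same two routes. MRE-negative subjects are told in writing that no such lesions were seen (sections 4.3.2, 5.2.1.2 and 5.2.2.2).

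**The earlier symptom measure.** Section 5.2.2.1 describes the mailing that asks for consent to read the scan: "The pack will also contain a BASDAI questionnaire with six simple questions relating to symptoms of axial inflammatory pain". Completion is optional, and the only use given is to judge selection bias.

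**The concern.** A PROM is a subjective report. If it is completed after the patient has learned the MRE result, and the message differs by result, part of any link between MRE and symptoms may come from being told. The planned test cannot separate that part from a real association.

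The question is open in the plan's own background. Section 2.1 cites one MRE study of 286 IBD patients with no correlation between MRE score and inflammatory back pain, and two dedicated-MRI studies in which most patients with sacroiliitis had such pain. A positive result from post-disclosure PROMs would not settle the matter.

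The study will already hold a BASDAI that the disclosure cannot have influenced, but the plan does not assign it to this analysis.

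**Working it through.** **Order of events for one patient**

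1. The consent pack arrives with the optional BASDAI (5.2.2.1).
2. The patient consents, and only then does the study read the scan (4.2.1).
3. The patient is told the result (4.3.1, 4.3.2).
4. The patient attends clinic and completes the five PROMs (4.1, 6.1, 6.2).

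A BASDAI returned with the consent therefore precedes the study's reading of that scan. The clinic PROMs follow disclosure.

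**The plan's own figure.** Section 8.1 expects about 445 scans and cites a prevalence of 15% to 16.7%. 445 × 0.15 = 66.75, which reproduces its figure of at least 66 cases and 66 controls. Rounded, the screened group divides into 67 positive and 445 − 67 = 378 negative. (445 is taken as printed. The adjacent figures give 990 × 0.50 = 495, which is a separate matter.)

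**Size of a possible disclosure effect.** The documents give no SD or reporting shift for any PROM, so the shift is assumed.

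- Standard error of a group difference at 66 v 66, in SD units: √(2/66) = 0.174.
- Shift of 0.2 SD: 0.2/0.174 = 1.15 standard errors. Shift of 0.3 SD: 0.3/0.174 = 1.72.
- With no true association, the two-sided rejection rate is Φ(shift/SE − 1.96) + Φ(−shift/SE − 1.96). This gives 5% at no shift, 9% at 0.1 SD, 21% at 0.2 SD and 41% at 0.3 SD. A simulation of 20,000 runs gave 21% at 0.2 SD and 40% at 0.3 SD.

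**Precision of the pre-review BASDAI.** The variance of the group difference relative to 66 v 66, with the same return proportion r assumed in both MRE groups, is

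(1/67 + 1/378) / (2/66) / r = (0.01757/0.03030)/r = 0.58/r.

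| Return r | Variance ratio |
|---|---|
| 100% | 0.58 |
| 75% | 0.77 |
| 60% | 0.97 |
| 58% | 1.00 |
| 50% | 1.16 |

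The difference detectable with 80% power at two-sided 0.05 is (1.96 + 0.84) × SE. That is 0.49 SD at 66 v 66. With the pre-review BASDAI it is 0.37 SD at full return, 0.43 SD at 75% and 0.53 SD at 50%. If the Assess phase reached only the plan's minimum of 60 per group, the break-even return would be 0.01757/(2/60) = 53%.

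**The case against.** **The time point is inferred.** Section 8.2 says only PROMs, and the pack BASDAI is itself patient-reported. A reader might infer that the plan commits to post-disclosure scores. It does not say so. The inference rests on the list of PROMs in sections 1.6 and 4.1 and on the single use given to the pack form. It is the likelier reading, but the firm fault is the unstated time point.

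**The form is optional.** A reader might infer that the whole screened group will have a pre-result score. All invited patients are sent one, but section 5.2.2.1 makes completion voluntary and gives no return rate. Return may also depend on symptoms. This stands, and it limits the precision argument.

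**The association is peripheral.** None of the five objectives in section 3.2 is a link between MRE score and symptoms. It is one pair in a list of association tests. This stands and sets the weight of the point.

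**The shift is assumed and the model simplified.** The calculation compares two groups, whereas section 8.2 plans a regression on a score. Patients are told whether lesions were seen, so disclosure bears on the positive/negative contrast and need not create a gradient among positives. This stands: the error rates show that bias can occur, not how large it will be.

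**The remedy is partial.** It covers one of five PROMs. Controls in the Assess phase are matched on age and sex, and the full screened group is not, so adjustment is needed. Patients with known SpA already carry a diagnosis when they fill in the pack form, so disclosure matters most in newly flagged cases. The clinician's help with the forms is not shown to differ by MRE group, and the postal form lacks that support. The other associations in section 8.2 are naturally served by same-visit PROMs.

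These points reduce the weight. They do not remove the reason to use a form that will be collected anyway.

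**Conclusion.** The point holds as a minor one. Section 8.2 leaves the PROM time point open. If the Assess-phase PROMs are used, knowledge of the MRE result could contribute to an association with symptoms, and the plan does not address this. How much is unknown. The 21% and 41% rejection rates depend on assumed shifts of 0.2 and 0.3 SD, a true association of zero and a simple 66 v 66 comparison.

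The case for the pre-review BASDAI is the removal of disclosure, and it also avoids the further selection of who attends after learning the result. Better precision is a conditional extra, available only above about 58% return. The measure still carries selection into screening consent.

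A reader might go further and conclude that the accuracy results are compromised. The documents do not support that from this point. Sensitivity, specificity and AUC compare MRE with dedicated axial MRI and clinical assessment, and they do not rest on the regression of MRE score against PROMs.

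**What to change.** In section 8.2:

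- State the time point of the PROMs used in each association.
- Analyse MRE score against the pre-review BASDAI in all screened subjects who return it, adjusted for age and sex, and interpret the MRE-BASDAI association from this analysis.
- Report the return rate by MRE group.
- Keep the clinic BASDAI, BASFI, VASbp, ASDAS and HAQ-DI analyses, and label them as post-disclosure.
- Where a subject has both BASDAIs, compare the change from screening to clinic by MRE status. Report the interval between them, because section 5.2.2.2 selects controls only after cases are enrolled.

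The cost is a few sentences in section 8.2 and data entry of a form that is already being posted. The downsides are voluntary return, cover of only one PROM, and lower precision than 66 v 66 if return falls below about 58%.

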6.1 MRE Review

Subjects who consent for the ProSpA-CD-Screen phase of the study will have their MRE images reviewed for evidence of axSpA

Subjects who then consent for the ProSpA-CD-Assess phase of the study will immediately undergo the following assessments:

6.2 Clinical questionnaires

BASDAI, BASFI, VASbp, ASDAS & HAQ-DI.

6.3 Clinical assessment and measurements

BASMI, tender and swollen joints, SPARCC enthesitis index, presence of skin and nail psoriasis.

